## 18.3 Informed Consent and HIPAA Compliance

In obtaining and documenting informed consent, the investigator should comply with the applicable regulatory requirement(s), and should adhere to GCP and to the ethical principles that have their origin in the Declaration of Helsinki. Prior to the beginning of the trial, the investigator should have IRB approval of the written ICF and any other written information to be provided to participants. Participants, their relatives, guardians, or authorized representatives and study partners will be given ample opportunity to inquire about the details of the study. Prior to a participant's participation in the trial, the written ICF should be signed and personally dated by the participant and by the person who conducted the informed consent discussion. Participants should be provided a copy of the signed ICF.

The informed consent will not only cover consent for the trial itself, but also for the genetic research, biomarker studies, biological sample storage and brain imaging. The consent for storage will include consent to access stored data, biological samples, and imaging data for secondary analyses. Consent forms will specify that DNA and biomarker samples are for research purposes only; the tests on the DNA and biomarker samples are not diagnostic in nature and participants will never receive results. MRI scan findings of clinical significance, determined by the site radiologist, can be shared with participants per Study Clinician discretion.

Consent forms will be developed by the ADCS Regulatory Affairs in collaboration with the PDs. The sample consent form provided to sites will include all of the required elements of informed consent required by the FDA. The sample consent form will be sent to participating sites where it should be tailored to include site-specific information to meet local IRB regulations. Each site PI, under the guidance of the local IRB, is responsible for ensuring that all applicable state laws are met with regards to judgment of competency and the consent form process. Each

participating site must submit a letter of IRB-approval and the approved consent form to Regulatory Affairs at the ADCS, along with other required regulatory records and essential documents in order to be approved to enroll participants into EXERT. During the first monitoring visit following participant enrollment, the ADCS clinical monitors will review the consent forms and verify that the proper signatures have been obtained.

### **18.3.1 Participant Confidentiality | HIPAA**

Information about study participants will be kept confidential and managed according to the requirements of HIPAA. HIPAA regulations require a signed HIPAA Authorization informing the participant of the following:

- What protected health information (PHI) will be collected from participants in this study
- Who will have access to that information and why
- Who will use or disclose that information
- The rights of a research participant to revoke their authorization for use of their PHI

In the event that a participant revokes authorization to collect or use PHI, the investigator, by regulation, retains the ability to use all information collected prior to the revocation of participant authorization. Each site PI, under the guidance of the local IRB, is responsible for ensuring that all applicable HIPAA regulations and State laws are met.

### **18.4 Genetic Research and Storage of Genetic Material**

The DNA is banked in locked freezers in the ADCS Biomarker laboratory at UCSD. Sample tubes are bar-coded and linked to PID only and banked without personal identifiers. The presence of the sample is recorded into a computerized inventory database that is managed by ADCS Informatics and is encrypted and password-protected.

Only DNA from consenting participants will be banked and used to facilitate future research on aging and dementia, particularly in the discovery of genetic polymorphisms that may influence risk of developing AD. Collection of DNA will permit ADCS investigators to probe candidate genetic polymorphisms as predictors of outcome in future studies. The samples will be stored by the ADCS as long as funding is available from the NIH. If funding should lapse completely, the UCSD ADRC will provide responsible custodianship of the ADCS biospecimen bank.

### **18.5 Storage of Biospecimen Samples**

All biospecimens banked for future AD biomarker research will be shipped to and stored by the ADCS Biomarker Core at UCSD. Sample tubes are bar-coded and linked to PID only and banked without personal identifiers. The presence of the sample is recorded into a computerized inventory database that is managed by ADCS Informatics and is encrypted and password-protected.

## **18.6 MRI Data Storage**

MRI scans will be labeled according to each site's imaging machine capabilities using PID and scanner specific series descriptions as detailed in the Technical Manual. All imaging data will be de-identified using participant identifiers as detailed in the Technical Manual and checked by the ADCS Imaging Core to confirm the absence of participant identifying information.

## **18.7 Inclusion of Children as Participants in Research Involving Human Subjects**

Children will not be included.

## **18.8 Study Monitoring**

The ADCS clinical monitors are responsible for inspecting the e-CRFs and source documents at regular intervals throughout the study to verify adherence to the protocol, completeness and accuracy of the data, and adherence to local regulations on the conduct of clinical research. An unblinded monitor will inspect documents pertaining to randomization, intervention implementation, and AEs. A blinded monitor will inspect all other source documents.

The monitoring visits must be conducted according to the applicable ICH and GCP guidelines to ensure protocol adherence, quality of data, drug accountability, compliance with regulatory requirements and continued adequacy of the investigational site and its facilities. The site investigator will cooperate in the monitoring process by ensuring the availability of the e-CRFs, source and other necessary documents at the time of the monitoring visits. The site PI will promptly address any matters brought to his/her attention by the monitor, and may be asked to meet in-person with the site monitor during monitoring visits.

## **19.0 AUDIT**

In accordance with ICH GCP, representatives of the ADCS and/or sponsor and/or regulatory agency may select this study for audit. The site PI and study staff are responsible for maintaining the site master file containing all study-related regulatory documentation as outlined by ADCS Regulatory Affairs that will be suitable for inspection at any time by ADCS, sponsor, its designees, and/or regulatory agencies. Inspection of site facilities (e.g., pharmacy, laboratories, YMCAs) to evaluate the trial conduct and compliance with the protocol may also occur.

## **20.0 RECORD RETENTION**

Essential documents and study records must be retained for a minimum of 7 years following primary publication of study results. The ADCS will notify sites when retention of such documents is no longer required.

## **21.0 PUBLICATION POLICY**

The results of this study will be published. To coordinate dissemination of data from this study, a publication committee will be formed. The committee will consist of the PDs, the Protocol Committee, interested site PIs, and appropriate ADCS personnel. The publication committee will solicit input and assistance from other investigators as appropriate and adhere to all ADCS Publications Policies.

## **22.0 SHARING OF FINAL RESEARCH DATA**

Data from this research will be shared with other researchers pursuant to the 02/26/2003 “Final NIH Statement on Sharing Research Data.” The ADCS grant contains a data sharing policy consistent with the goals of the NIH that also respects the rights of commercial partners. The NIH policy can be found at: <http://grants.nih.gov/grants/guide/notice-files/NOT-OD-03-032.html>.

The NIH endorses the sharing of final research data to serve these and other important scientific goals. To protect participants’ rights and confidentiality, identifiers will be removed from the data before they are shared.

**APPENDIX 1: SCHEDULE OF EVENTS**

| Visit Number                                                                           | 0        | 1         | 2        | 3     | 4              | 5     |
|-----------------------------------------------------------------------------------------------|-----------------|------------------|-----------------|--------------|-----------------------|--------------|
| Visit Name / Month                                                                     | Screen I | Screen II | Baseline | 6     | 12 | 18    |
| Visit Window (weeks)                                                                   |                 |                  |                 | +/- 2 | +/- 2          | +/- 2 |
| Brief Informed Consent for Screen I (screening for Screen II)                                 | X               |                  |                 |              |                       |              |
| Informed Consent for Enrollment, HIPAA                                                        |                 | X                |                 |              |                       |              |
| EXERT TAPA (to confirm sedentary status)                                                      | X               |                  |                 |              |                       |              |
| Review Inclusion & Exclusion Criteria                                                         | X               | X                |                 |              |                       |              |
| Demographics                                                                                  | X               | X                |                 |              |                       |              |
| Medical History                                                                               | X               | X                |                 |              |                       |              |
| Medication Review                                                                             | X               | X                | X               | X            | X                     | X            |
| Brief Physical Exam                                                                           |                 | X                |                 | X            | X                     | X            |
| Vital Signs                                                                                   |                 | X                | X               | X            | X                     | X            |
| Height                                                                                        |                 | X                |                 |              |                       |              |
| Weight                                                                                        |                 | X                | X               | X            | X                     | X            |
| Brief Neurological Exam                                                                       |                 | X                |                 | X            | X                     | X            |
| Modified Hachinski                                                                            |                 | X                |                 |              |                       |              |
| Fasting Clinical Blood Labs                                                                   |                 | X                |                 |              | X                     | X            |
| Blood Collection for ApoE Genotyping, & DNA Banking                                           |                 | X                |                 |              |                       |              |
| Fasting Blood Collection for Banking                                                          |                 |                  | X               | X            | X                     | X            |
| AE Monitoring at Clinic                                                                       |                 |                  | X               | X            | X                     | X            |
| 12-Lead Resting ECG                                                                           |                 | X                |                 |              |                       |              |
| 3MSE/MMSE                                                                                     |                 | X                |                 |              | X                     |              |
| Logical Memory I and II                                                                       |                 | X                |                 |              |                       |              |
| Auditory Verbal Learning Test                                                                 |                 | X                |                 |              |                       |              |
| ADAS-Cog13                                                                                    |                 |                  | X               | X            | X                     | X            |
| Trail-Making Test, DSST, Category and Letter Word Fluency                                     |                 |                  | X               | X            | X                     | X            |
| Computer Tests: NIH Toolbox (Flanker, DCCS), Cogstate (DET, IDN, OCL, OBK, GMLT, FNAME, BPSO) |                 |                  | X               | X            | X                     | X            |
| CDR                                                                                           |                 | X                |                 | X            | X                     | X            |
| ADCS-ADL-MCI, BRIEF-A, NPI (staff-administered questionnaires)                                |                 |                  | X               | X            | X                     | X            |
| GDS (self-administered questionnaire)                                                         |                 | X                |                 |              |                       |              |
| Cognitive Change Index (self-administered questionnaire)                                      |                 | X                |                 | X            | X                     | X            |
| SF-36, EQ5D (self-administered)                                                               |                 |                  | X               | X            | X                     | X            |
| Research Satisfaction Survey (self-administered)                                              |                 |                  | X               | X            | X                     | X            |
| Study Partner Self-Assessment Questionnaire                                       |                 |                  | X               | X            | X                     | X            |
| 400 m Walk Test                                                                               |                 | X                |                 | X            | X                     | X            |
| Structural/Functional MRI                                                         |                 | X                |                 |              | X                     |              |
| LP for CSF Collection and Banking                                                 |                 |                  | X               |              | X                     |              |

| Visit Number                                                                                             | 0        | 1         | 2        | 3     | 4               | 5     |
|----------------------------------------------------------------------------------------------------------|----------|-----------|----------|-------|-----------------|-------|
| Visit Name / Month                                                                                       | Screen I | Screen II | Baseline | 6     | 12  | 18    |
| Visit Window (weeks)                                                                                     |          |           |          | +/- 2 | +/- 2           | +/- 2 |
| Post-LP Safety Telephone Follow-Up                                                           |          |           | X        |       | X               |       |
| Replace Battery in Heart Rate Monitor                                                                    |          |           |          | X     | X               | X     |
| Dispense Physical Activity Logs                                                                          |          |           | X        | X     | X               |       |
| Retrieve/Review Physical Activity Logs                                                       |          |           | X        | X     | X               | X     |
| Actigraphy Recording Initialization (dispense device)                                        |          | X         |          | X     | X               | X     |
| Actigraphy Device Retrieval (10 days later)                                                  |          |           | X        | X     | X               | X     |
| Telephone Call to Participant by Clinic YMCA Liaison (query AEs, obtain medication updates)  |          |           | X        | X     | X               |       |
| Trainer-Supervised Exercise Sessions                                                         |          |           | X        | X     | X               |       |
| Trainer-Administered Rating of Perceived Exertion                                            |          |           | X        | X     | X               |       |
| Trainer-Administered AE Checklist                                                           |          |           | X        | X     | X               |       |
| Randomization                                                                                            |          |           | X        |       |                 |       |
| Treatment Blinding Questionnaire                                                                         |          |           |          |       | X               | X     |
| Provide Study Close-Out Materials                                                                        |          |           |          |       |                 | X     |

 Following Month 12 assessment, participants continue with their assigned exercise program but without supervision in Months 13-18

 The Study Partner Self-Assessment Questionnaire is comprised of the SF-36, the Pittsburgh Sleep Quality Index, the Insomnia Severity Index, the EQ5D, and questions about healthcare utilization

 Screening MRI to be conducted following site PI confirmation that participant has met all other inclusion/exclusion criteria; fMRI sequences added to protocol for approved sites

 To be completed for fasting participants who agree to LP at Baseline and Month 12

 Logs reviewed by Trainers weekly (in months 1-12), and by Clinic YMCA Liaison monthly when retrieved from YMCA (months 1-18) to identify potential adherence issues

 See Section 9.0 for visit-specific instructions

 Telephone call to be completed monthly (months 1-18)

 Supervision provided by study-certified YMCA Trainers, beginning after randomization through Month 12; data collected include type of exercise completed, exercise duration, HR, RPE, and other intervention-specific details (e.g., body parts stretched, treadmill speed and grade)

 Rating scale administered as part of every supervised exercise session (months 1-12) to assess effort and estimate exercise intensity

 Administered once per week by YMCA Trainer during supervised sessions to query change in health status in the preceding 7 days; faxed to clinic for triage and data entry within 24 hours of the session

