### **4.2 Potential Risks**

Although regular physical activity and exercise have numerous health benefits on blood circulation, metabolism, lipoprotein profile, bone mass, risk of falling and disease, high-intensity exercise can be associated with greater risk of adverse cardiovascular events, as

well as orthopedic and soft tissue (muscle, tendon, cartilage) injury. High-intensity exercise is also associated with lower adherence to a training regimen than lower-intensity exercise. Evidence favoring high-intensity over moderate-intensity exercise, however, is provided by a recent joint report by the ACSM and the American Heart Association showing greater risk reduction for cardiovascular disease and all-cause mortality. The EXERT protocols of moderate/high intensity aerobic training are consistent with the latest ACSM exercise recommendations for older adults. Risk of injury is strongest for overweight and unfit older adults. When sedentary adults begin to walk or jog, they may develop foot, leg, and knee injuries when training is performed more than 3 days per week and for more than 30 minutes per session; while prolonged exercise may result in overuse-related orthopedic injuries. The EXERT protocol that includes gradual increments of exercise intensity and duration, under the supervision of a trainer and taking into account individual needs and limitations, is in accordance with this recommendation and its safety has been established in other community-based exercise programs. In previous pilot exercise studies in MCI on which the protocol is based, of the 100 enrollees who completed the high-intensity arm (meeting all EXERT inclusion criteria), only 3 subjects (3%) were dropped due to a cardiovascular adverse event (AE) (follow-up tests indicated chronic disease pre-dating study entry for all 3 adults).

There are no known risks associated with participation in the SBR control group.

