### **6.2.3 Adverse Event Reporting by YMCA Trainers**

The AE Checklist will be completed weekly during a Trainer-supervised exercise session. This survey will query change in health or physical status in the last week, and will include questions to identify potential SAEs (death, life-threatening, hospitalization, disability or permanent damage). The AE Checklist will also query TEAEs, which most commonly include muscle or joint aches including flare-ups of pre-existing musculoskeletal conditions (e.g., arthritis, foot bone spurs or neuromas). The AE Checklist will be faxed to the clinic to permit review by the Study Clinician within 24 hours of AE notification by the participant.

Response to emergent serious or life-threatening medical events that occur while the participant is exercising at the YMCA will follow standard YMCA protocols that apply to the management of these events for any member of the facility. When appropriate, using the best judgment of YMCA staff, the EMS may be engaged to stabilize and transport an individual to a nearby

hospital for treatment. Other standard YMCA protocols may be used in the event of an onsite injury or medical event.

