### 6.4 Adherence

Adherence will be assessed using several strategies, including Physical Activity Log entries, and adherence outcomes obtained during the supervised sessions that include attendance, type of activity completed, exercise duration, time in target HR zone, subjective ratings of perceived effort, and achieved HR.

The Intervention Oversight Team has extensive experience implementing behavioral management strategies to support a positive exercise environment. The goal in EXERT will be for participants to complete at least 80% of the prescribed exercise sessions. Participants who miss a supervised exercise session will be contacted by the Trainer to confirm that the participant will attend the next scheduled supervised session. Participants who miss 2 consecutive supervised sessions for any reason will be contacted by the Trainer or Y-PM to problem-solve issues that obstruct attendance, provide encouragement, and schedule the next supervised session. For these cases, the Intervention Oversight Team may contact the Y-PM and Clinic YMCA Liaison to discuss strategies to increase adherence. Participants who do not

attend at least 10 supervised or unsupervised sessions per month will be counseled to improve attendance, and motivational strategies to increase adherence and limit obstacles to study participation will be implemented if necessary (e.g., goal setting, reinforcers identified and scheduled, etc.). In the first 12 months of the intervention, participants without an excused leave of absence who miss 48 exercise sessions within a 3-month period will be dropped from the intervention due to non-compliance.

If a participant misses a supervised exercise session for reasons that are unplanned (excludes missed visit for holiday closure, weather, and other anticipated reasons), a Missed Visit CRF will be completed by the Trainer and uploaded to the EDC by the Y-PM to permit tracking of these events.

For planned travel, total time away must be no more than a total of 2 months over the course of the study, and no more than 1 month at any one time to be considered for study entry. Participants must be willing to continue the assigned exercise unsupervised if travelling out of the area for more than 1 week. For all planned absences, the Trainer will meet with the participant in advance to develop an acceptable program for continued exercise.

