## 6.6 Temporary Intervention Discontinuation

There may be situations that arise that will warrant temporary discontinuation of the intervention for a participant. When these events occur, the Intervention Oversight Team, Y-PM, Trainer, and Clinic YMCA Liaison will develop a plan during twice per month meetings to keep the participant engaged in the study while 'on hold' and to reengage the participant once the situation has resolved. The decision to remove a participant from the study in the event of a prolonged Temporary Intervention Discontinuation will be made by the Intervention Oversight Team, in consultation with the site PI and the ADCS, on a case-by-case basis.

A participant will be classified as being medically 'on hold' if 4 or more consecutive exercise sessions are missed due to self-reported hospitalization, injury or other health issue (vacations excluded), or is withdrawn from physical activity as per primary care provider (PCP) orders. If a participant is on hold, the Trainer, Y-PM, or Clinic YMCA Liaison will contact the participant weekly to obtain updates about status and expected schedule when exercise can be resumed.

Restart following soft tissue injuries without surgery can occur when the participant self-reports an ability to continue the intervention. Restart following other medical complications will require prior approval by the Study Clinician. The site PI may choose to obtain the participant's PCP approval for re-start as well. Communication with participants on medical leave regarding their status in the study should always emphasize that they are 'on hold' rather than 'temporarily suspended' or 'on leave' to encourage continued psychological/emotional commitment to the study, which will likely expedite restart when appropriate to do so.

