### 13.2 YMCA Study Team (see Section 6.2.1)

## 14.0 ADVERSE EVENTS

Potential AEs for study-related activities and interventions are described to each participant by trained clinic staff during the informed consent process. Participants are instructed to report the occurrence of an AE to the Clinic YMCA Liaison or Study Clinician. Participants will also be instructed to report AEs to the YMCA Trainers during supervised exercise sessions.

Trainers will complete the AE Checklist with participants once per week during a supervised exercise session. The AE Checklist will be faxed to the clinic to permit review and data entry of Study Clinician-verified AEs within 24 hours of reporting, and AE medical management as needed. AEs will also be queried at each clinic assessment visit, and during the monthly telephone call by the Clinic YMCA Liaison.

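### The weekly AE Checklist lapses when a participant misses supervised sessions, so non-serious AEs are sought harder in attended weeks and the AE comparison may be biased if attendance differs between arms

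*Protocol*

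**What the plan says.** Protocol 6.2.3 states: "The AE Checklist will be completed weekly during a Trainer-supervised exercise session". Appendix 1, footnote 10, gives the same setting and fixes the look-back: "Administered once per week by YMCA Trainer during supervised sessions to query change in health status in the preceding 7 days". Section 11.9.2 agrees, with a look-back of the last week. No section describes a checklist for a week in which no supervised session was attended, or a catch-up question afterwards.

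Other routes exist. Section 14.0 states: "AEs will also be queried at each clinic assessment visit, and during the monthly telephone call by the Clinic YMCA Liaison". Appendix 1, footnote 7, runs that call through months 1 to 18. Section 14.0 also relies on self-report: "Participants are instructed to report the occurrence of an AE to the Clinic YMCA Liaison or Study Clinician".

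Two further contacts follow absence. In Section 6.4, "Participants who miss a supervised exercise session will be contacted by the Trainer", and the stated purpose is to confirm attendance at the next session. In Section 6.6, once a participant is medically on hold, the Trainer, the YMCA Project Manager or the Clinic YMCA Liaison "will contact the participant weekly to obtain updates about status and expected schedule when exercise can be resumed". Neither contact is specified as an AE query.

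SAP 15.1 summarises event and participant counts by arm. SAP 15.2 compares the number of participants with at least one AE by Fisher's exact test. Neither mentions checklist completion or attendance.

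**The concern.** An AE can itself keep a participant away, and staying away removes the weekly question. Section 6.2.3 names muscle and joint aches as the most common events. These are often brief, and in participants with amnesic MCI a call looking back about four weeks is likely to recover fewer of them than a 7-day question.

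Long gaps are possible. Section 6.4 drops a participant for non-compliance after 48 missed sessions in 3 months. With a month of exactly 4 weeks (Section 6.3), 3 × 4 × 4 = 48, which is every session. Planned travel may last a month at a time.

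Section 4.2 gives a reason to expect a difference between arms: "High-intensity exercise is also associated with lower adherence to a training regimen than lower-intensity exercise". If attendance is lower with aerobic exercise and the other routes do not make up the gap, the AE comparison would tilt towards making aerobic exercise look safer. The planned tables would not show whether this had happened.

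**Working it through.** The plan states no figure on this point, so there is nothing to reproduce. The check asks how large the effect could be under stated assumptions.

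**From the documents.** Two supervised sessions per week after week 2, through Month 12 (Protocol 6.1). Attendance goal of 80% of prescribed sessions (Protocol 6.4). Per-protocol threshold of 70% of supervised sessions (SAP 6.2). I use 80% and 70% as an illustrative contrast between arms; neither document predicts it.

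**Assumed.** Equal true AE rates in both arms, and a share *r* of the events in uncovered weeks found by the other routes.

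**Step 1: weeks without a checklist.** At attendance *a*, the uncovered share is (1 − *a*)² if absences are independent and 1 − *a* if whole weeks are missed.
- 80%: 4% to 20%
- 70%: 9% to 30%
- 60%: 16% to 40%

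**Step 2: share of events captured.** With checklist coverage *c*, captured share *S* = *c* + (1 − *c*)*r*. The ratio is *S* in the lower-attending arm over *S* in the higher-attending arm.

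| Contrast | r = 0 | r = 0.5 | r = 0.8 | r = 1 |
|---|---|---|---|---|
| 80% v 70%, independent | 0.91/0.96 = 0.95 | 0.955/0.98 = 0.97 | 0.982/0.992 = 0.99 | 1.00 |
| 80% v 70%, whole weeks | 0.70/0.80 = 0.88 | 0.85/0.90 = 0.94 | 0.94/0.96 = 0.98 | 1.00 |
| 80% v 60%, whole weeks | 0.60/0.80 = 0.75 | 0.80/0.90 = 0.89 | 0.92/0.96 = 0.96 | 1.00 |

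The column *r* = 0 means that monthly calls, visits and self-report find nothing. It is a bound, not an expectation.

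**Step 3: the test the SAP plans.** Assume Poisson counts with mean *m* AEs per participant. The proportion with at least one recorded AE is 1 − exp(−*mS*). For 80% v 70% with whole-week absences:
- *m* = 1: 0.5034/0.5507 = 0.914 at *r* = 0; 0.5726/0.5934 = 0.965 at *r* = 0.5
- *m* = 3: 0.8775/0.9093 = 0.965 at *r* = 0; 0.9219/0.9328 = 0.988 at *r* = 0.5

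The matching event-count ratios are 0.88 and 0.94, so the planned test is distorted less.

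**Step 4: a tempting correction that misleads.** Suppose AEs from all routes are divided by completed checklist-weeks, again at 80% v 70% coverage and a true ratio of 1.0. At *r* = 0.5 the result is (0.85/0.70)/(0.90/0.80) = 1.08. At *r* = 1 it is (1/0.70)/(1/0.80) = 1.14. The bias is now upward for the lower-attending arm.

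**The case against.** A reader might infer that missed weeks are never covered and that harms of aerobic exercise are under-counted. The documents do not support either statement.

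The gap belongs to one instrument. The monthly call and the clinic visits do not depend on session attendance, and participants are told to report AEs themselves. Absence through injury or illness leaves further traces. On-hold status is triggered by the health problem itself and brings weekly contact (6.6). The reason for temporary discontinuation is coded, with an adverse-experience category (6.7). An unplanned missed supervised session generates a form, and two consecutive misses trigger a problem-solving contact (6.4). Physical inability to carry out the intervention is by definition an AE (14.1). Serious events of any cause must be reported within 24 hours of learning of them, whatever the exposure (15.2).

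Nor is a difference between arms established. Section 6.3.1 cites adherence above 90% in previous exercise trials, and one attended supervised session is enough to cover a week. In months 13 to 18 neither arm has supervised sessions, so the checklist cannot differ between arms then.

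All of this stands, and it narrows the point to mainly minor, non-serious AEs in months 1 to 12. It does not remove it. The missed-session and on-hold contacts are not specified as AE queries, on-hold contact generally begins only after four consecutive health-related misses or a physician's order, and the SAP plans nothing that would show whether ascertainment was balanced.

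**Conclusion.** The point holds as a possible bias. Followed as written, the most frequent AE query depends on attendance, its 7-day look-back leaves missed weeks to less frequent or passive routes, and the AE comparison takes no account of this.

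Bias requires both unequal attendance and incomplete capture by the other routes. Section 4.2 makes the first plausible and suggests the direction; neither document measures either. In the 80% v 70% illustration the captured-event ratio lies between 0.88 and 1.00, and is 0.98 or above if the other routes find at least 80% of events in uncovered weeks. The at-least-one-AE test is affected less than event counts. These figures rest on assumed attendance, assumed *r*, equal true rates and, in Step 3, a Poisson model. They show possible size and are not estimates for this trial.

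**What to change.** **Protocol.** Word the checklist question as *since your last checklist*. Ask it during the contacts already made after a missed supervised session (6.4) and while a participant is on hold (6.6), by whichever of the Trainer, YMCA Project Manager or Liaison makes the contact. The cost is one wording change and a few minutes on existing calls. The downside is a slightly longer look-back at some sessions.

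**SAP section 15.**
- Report checklist completion by arm or, if completion was not stored, weeks with an attended supervised session.
- Report AEs by reporting source.
- Add a sensitivity comparison limited to AEs found by routes not tied to attendance: monthly calls and clinic visits. An event found by both a checklist and a call should count here; otherwise earlier detection by checklist would remove more events from the better-attending arm.
- If checklist-weeks are used as exposure, count only checklist-detected AEs in the numerator, for the reason in Step 4.

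For data already collected, only the SAP part applies. It costs a few tables, provided that reporting source can be recovered from the AE records; the documents do not say whether it was stored.
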